## 10.6 Appendix 6: Neurological examination checklist

Unless otherwise stated, each aspect of the neurological examination will be categorised into normal, abnormal or not evaluated.

### General

Level of consciousness

### Cranial Nerves

Pupillary reaction to light  
Visual fields  
Visual acuity (normal, corrected, abnormal, not evaluated)  
Eye movements  
Facial sensation  
Facial movement (smile)  
Hearing (finger rub)  
Palate/gag (say “ahhh”)  
Tongue movement  
Trapezius (shoulder shrug)

### Tone

Upper Extremity Left  
Upper Extremity Right  
Lower Extremity Left  
Lower Extremity Right

### Strength

Upper Extremity Left  
Upper Extremity Right  
Lower Extremity Left  
Lower Extremity Right

### Reflexes

Biceps Left  
Biceps Right  
Triceps Left  
Triceps Right  
Knee Left  
Knee Right  
Ankle Left  
Ankle Right

### Sensory

Cold  
Pin prick  
Light touch  
Proprioception (toe up/down)

Protocol  
Trial ID: NN7088-4595~~CONFIDENTIAL~~Date:  
Version:  
Status:  
Page:05 July 2021  
4.0  
Final  
94 of 102***Novo Nordisk*****Gait**

Gait walking  
Gait running  
Gait on heels  
Gait on toes  
Tandem (toe/heel walk)  
Stand on one leg (right)  
Stand on one leg (left)  
Hop on one foot (right)  
Hop on one foot (left)  
Rhomberg sign (normal [absent], abnormal [present], not applicable)

**Coordination and Fine Motor**

Finger-to-nose (right)  
Finger-to-nose (left)  
Rapid index finger tap (right)  
Rapid index finger tap (left)  
Rapid finger movement (right)  
Rapid finger movement (left)

Adapted from Paediatric Stroke Outcome Measure (PSOM)

## 10.7 Appendix 12: Country-specific requirements

The following items are applicable for China.

Item	Section	Section title	Local requirement
1	5.1 and 5.2	Inclusion/Exclusion criteria	The criteria will be assessed at the investigator's discretion unless otherwise stated.
2	10.1	Appendix 1: Regulatory, ethical, and trial oversight considerations	Any trial procedure conducted in China mainland should comply with "Regulations on management of Human Genetic Resources of People's Republic of China" and relative guideline. http://www.gov.cn/zhengce/content/2019-06/10/content_5398829.htm
3	10.1.10	Retention of clinical trial documentation	Site specific data should only be stored at site. Long term storage of Chinese Patients' Trial Data is not allowed in other entities.
4	10.5	Appendix 12: Country-specific requirements	The samples which are tested at central lab will be destroyed as biological waste according to local regulation and lab manual. The laboratory samples for Chinese patients will be destroyed no later than the finalization of the clinical trial report, or according to local regulatory requirement.

## 10.8 Appendix 13: Abbreviations

ABR	annualised bleeding rate
AE	adverse event
AESI	adverse event of special interest
ALT	alanine aminotransferase
AST	aspartate aminotransferase
BP	blood pressure
CRF	case report form
CTR	clinical trial report
DFU	directions for use
DMC	data monitoring committee
DRE	disease related event
DUN	dispensing unit number
ECG	electrocardiogram
eCRF	electronic case report form
ED	exposure day
eGFR	estimated glomerular filtration rate
FAS	full analysis set
FDA	U.S. Food and Drug Administration
FDAAA	FDA Amendments Act
GCP	Good Clinical Practice
HCP	host cell protein
HIV	human immunodeficiency virus
ICH	International Council for Harmonisation
IEC	independent ethics committee
IMP	investigational medicinal product
IRB	institutional review board
i.v.	intravenous(ly)
IWRS	interactive web response system
LAR	legally acceptable representative (also referred to as 'caregiver')
LOCF	last observation carried forward

LPLV	last patient last visit
MDRD	Modification of Diet in Renal Disease
MIDF	monitor-initiated discrepancy form
NIMP	non-investigational medical product
PCD	primary completion date
PEG	polyethylene glycol
PTP	previously treated patient
rFVIII	recombinant factor VIII
RNA	ribonucleic acid
SAE	serious adverse event
SAP	statistical analysis plan
SUSAR	suspected unexpected serious adverse reaction
TEAE	treatment emergent AE
TMM	trial materials manual
WFH	World Federation of Hemophilia
WOCBP	woman of child bearing potential

## 10.9 Appendix 14: Protocol amendment history

The Protocol amendment summary of changes table for the current protocol version is located directly before the table of contents.

### Protocol version 2.0 (28 Sep 2020)

The overall rationale for preparing the protocol version 2.0 was to correct inconsistencies and editorial errors observed.

Section # and name	Description of change	Brief rationale
Synopsis section 1.1 and Section 5.2 Exclusion criteria	Exclusion criterion 7 updated	The criterion updated for more clarity.
Section 1.2 Flow chart and Table 1-1	Addition of Height, weight and BMI to the flow chart. Deletion of drug dispensing at visit 7 and other minor updates	Added for clear instruction on assessments and duplicate coagulation parameter assessment removed and other typographical errors corrected
Section 4.1.1 Treatment of patients  Section 8.1.1.1 Definition of severity of bleeding episodes  Section 8.5.1 visit 2a for patients undergoing PK assessments.  Section 8.5.3 visit 7 for patients undergoing PK assessments  Section 8.7 Diary  Section 8.8 Home treatment training  Section 10.17 Dissemination of clinical trial data	Minor updates	Typo corrected and minor information added
Section 6.1 Treatments administered	Some text deleted	Text deleted to align with trial material manual
Section 6.3 Measures to minimise bias: Randomisation and blinding	Some text deleted	Section updated to reflect the actual scenario in the trial.
Section 6.4.1 In-use time	New section added	Added to highlight importance of in-use time of the trial product

Section # and name	Description of change	Brief rationale
Section 7.1 Discontinuation of trial treatment	Errors corrected in this section	Section updated and errors corrected.
Section 7.2 Patient withdrawal from the trial	Text corrected	Text aligned with section 7.1 and duplicate text removed
Section 8.2.1 physical examination	Additional information on Height, Weight and BMI assessments added	Information was missed previously
Section 8.2.3 Clinical safety laboratory assessments	Duplicate text deleted	Duplicate text deleted as the text is already available in appendix 2.
Section 8.6.1 FVIII inhibitors	Text added with information about inhibitor liability and some text corrected	Text added for more clarity
Section 10.2, Appendix 2	Blood volume in table 10.1 and 10.2 corrected and other minor updates	Information corrected
Section 10.3.3 Description of AESI and AEs requiring additional data collection	Definition of anaphylactic reaction updated	Missing text added
Section 10.3.5 Reporting of SAEs	Figure 10.1 updated with missing timelines	Typo corrected

**Novo Nordisk**

## Version history

This Statistical Analysis Plan (SAP) for trial NN7088-4595 is based on the protocol *A multi-centre, open-label trial evaluating efficacy, safety and pharmacokinetics of turoctocog alfa pegol (N8-GP) when used for treatment and prophylaxis of bleeding episodes in previously treated Chinese patients with haemophilia A*, version 3.0 dated 21Jan2021.

**Table 1 SAP Version History Summary**

SAP Version	Approval Date	Change	Rationale
1		Not Applicable	Original version
2		
A few re-wordings in Sections 5.3, 5.4.2 and 5.4.3
 
Addition of ECG to Section 5.6 Other safety analyses
	
Clarification of existing text
 
In order to accommodate a request from China Center for Drug Evaluation

## 1 Introduction

The rationale for this Phase 3b trial is to assess the effect of N8-GP in Chinese patients with severe haemophilia A (FVIII activity <1%) previously treated with other FVIII product(s) (PTPs). The aim is to accumulate sufficient exposure data in order to evaluate efficacy and safety of N8-GP in treatment and prevention of bleeding episodes and to obtain N8-GP PK data in this patient population.

Specifications of tables, figures and listings (TFL) and other specifications not included in this SAP will be described in the mock TFL.

### 1.1 Objectives and endpoints

#### Primary objective

- To evaluate the clinical efficacy of N8-GP in bleeding prophylaxis (number of bleeding episodes during prophylaxis) in Chinese adolescent and adult patients with severe haemophilia A previously treated with other FVIII products

#### Secondary objectives

In Chinese adolescent and adult patients with severe haemophilia A previously treated with other FVIII products,

- To evaluate the clinical efficacy of N8-GP when used for treatment of bleeding episodes
- To evaluate the immunogenicity of N8-GP
- To evaluate the general safety of N8-GP
- To evaluate the consumption of N8-GP
- To evaluate the pharmacokinetic properties of N8-GP

### 1.2 Trial design

This trial is a multi-centre, open-label, non-randomised, single-arm phase 3b trial evaluating the clinical efficacy, safety (including immunogenicity) and PK of N8-GP when used for treatment and prevention (prophylaxis) of bleeding episodes in Chinese patients  $\geq 12$  years of age with severe haemophilia A (FVIII activity <1%). This trial design is overall similar to the design of the completed global, pivotal pathfinderTM2 trial in adult and adolescent previously treated patients with severe haemophilia A (trial NN7088-3859).

Statistical Analysis Plan  
Trial ID: NN7088-4595  
UTN: U1111-1235-5905  
EudraCT No: 2020-003001-58

**CONFIDENTIAL**

Date: 29 January 2021 | **Novo Nordisk**  
Version: 2.0  
Status: Final  
Page: 6 of 18

Thirty-six (36) Chinese PTPs with severe haemophilia A, aged  $\geq 12$  years and with  $\geq 150$  exposure days (EDs) to other FVIII product(s), will receive prophylaxis with 50 IU/kg N8-GP every 4 days (with the possibility of switching to twice-weekly dosing during the treatment period at the discretion of the Investigator). Bleeding episodes will be treated with bolus injection(s) of 20-75 IU/kg N8-GP.

The treatment period in the trial will be at least 28 weeks with N8-GP prophylaxis every 4 days where  $\geq 50$  EDs to N8-GP (including treatment of bleeding episodes) must be obtained. The screening period will be 2 weeks and the follow-up period will be 30 days.

At least 30 patients must complete the trial with  $\geq 50$  EDs to N8-GP (including treatment of bleeding episodes) and  $\geq 6$  months ( $\geq 28$  weeks) of prophylaxis.

Please refer to the protocol for more details.

Statistical Analysis Plan  
Trial ID: NN7088-4595  
UTN: U1111-1235-5905  
EudraCT No: 2020-003001-58

~~CONFIDENTIAL~~

Date:  
Version:  
Status:  
Page:

29 January 2021  
2.0  
Final  
7 of 18

**Novo Nordisk**

## 2 Statistical hypotheses

No confirmatory hypotheses are planned to be tested due to the low number of patients to be included in this trial.

## 3 Sample size determination

No formal sample size calculations have been performed. Based on meeting communication with CDE and with the supplement data from the global pivotal trial NN7088-3859 which also included Asian patients, a total number of 30 Chinese patients to complete this trial is considered sufficient to evaluate efficacy and safety in the Chinese population.

Fifteen (15) patients will participate in PK assessments sessions to ensure at least 12 patients with complete single-dose and steady-state PK profiles.

## 4 Analysis sets

All patients exposed to N8-GP in this trial will be included in the full analysis set (FAS) and the safety analysis set (SAS).

Exceptional outlier pharmacokinetic profiles and/or individual plasma FVIII activities may be excluded when analysing pharmacokinetic endpoints based on the FAS. The rules to exclude data points from analysis of pharmacokinetic endpoints are described in this SAP, and the decision of data exclusion will be made during a review prior to database lock. Any excluded data points will be documented in the database lock minutes and also in the clinical trial report (CTR).

## 5 Statistical analyses

### 5.1 General considerations

Novo Nordisk will be responsible for the statistical analyses. The statistical analysis plan (SAP) will be finalised prior to first patient first visit.

Summaries for continuous endpoints will include total number (N), mean (SD), median and min/max, and for pharmacokinetic endpoints also geometric mean and coefficient of variation (CV%). Summaries for categorical endpoints will include N, number (n) and percentages (%) for each outcome category.

In general, all summaries and analyses will also be prepared by age subgroup (12-17 and 18-70 years of age).

FVIII activities below lower limit of quantification (LLOQ) will be set to half the value of the LLOQ.

All bleeding endpoints will be evaluated based on bleeding episodes requiring treatment with N8-GP. Non-treatment requiring bleeding episodes will only be listed. Bleeding episodes in relation to surgery will also only be listed, i.e. not included in the analysis of bleeding endpoints.

Multiple bleeding locations occurring from the same event (e.g. due to a bicycle accident) or at the same time point will be counted as one bleeding episode and only one haemostatic response will be considered for the bleeding episode. In case different responses were registered for different bleeding locations in such a bleeding episode, the worst response will be used in the analysis.

A re-bleed is defined as a worsening of symptoms in the same location after an initial period of improvement, either on treatment or within 72 hours after stopping treatment. If a bleed occurs in the same location later than 72 hours after stopping the treatment it is considered a new bleed. Re-bleeds will only be considered for joint bleeds since the specific location for other bleeds e.g. in subcutaneous are not captured in the database.

In the sub analyses of annualised bleeding rate where there are less than 5 patients in a sub-group, model based estimation will not be done. If no bleedings occur in a sub-group, then the confidence interval will not be calculated.

For patients that discontinue treatment with N8-GP, data after visit P8 will only be included in listings and clearly marked. For secondary safety endpoints separate summary tables for data relating to the period after visit P8 will be prepared if such data is available for 5 or more patients.

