addition, prophylactic treatment can be time consuming. While prophylaxis is the standard of care for haemophilia, patients often face challenges integrating prophylaxis dosing into their daily life. Thus, therapies that require less frequent dosing may reduce the overall burden of prophylaxis. Currently, there are no extended half-life rFVIII products available in China, therefore Chinese patients will still be facing the above-mentioned barriers.

With the well-established knowledge of N8-GP efficacy and PK properties obtained from the comprehensive global clinical development program in severe haemophilia A patients across all age groups, N8-GP provides a new treatment option to significantly reduce the dosing frequency associated with regular prophylaxis, which fulfils the urgent unmet needs in Chinese patients.

Turoctocog alfa pegol (in this protocol referred to as 'N8-GP'), a 40-kDa glycoPEGylated human recombinant coagulation factor VIII (rFVIII) with an extended half-life, has been developed to offer patients with haemophilia A a more effective and less burdensome treatment versus standard FVIII products. N8-GP has improved PK properties including a 1.6-fold increase in terminal half-life compared with standard FVIII products, which offers the possibility of achieving FVIII levels in the range of moderate haemophilia A with a less-burdensome every fourth day treatment regimen. With a better overall PK profile and the ability to sustain higher FVIII levels than standard therapies, N8-GP has the potential to improve prophylaxis and simplify management of bleeds as well as perioperative haemostatic control in patients with haemophilia A.

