**Novo Nordisk**

Title	Time frame	Unit	Details
AUC (0-t)	0–96 h post-injection at visit 2a and visit 7	h*(IU/mL)	
Area under the plasma activity versus time profile from time zero to the last measurable activity. Measure of plasma exposure in the time interval 0 to last measurable activity.
 
AUC(0-t) is calculated using the linear trapezoidal method from time 0 to the time for the last measurable activity. The activity at time 0 will be estimated by log-linear back extrapolation of the two initial post-administration activities. If the second value is not lower than the first value, the concentration at time 0 will be defined as the highest of these two.

AUC (0-96h)	0–96 h post-injection at visit 2a and visit 7	h*(IU/mL)	
AUC(0-96h) is calculated using the linear trapezoidal activities. If FVIII activities are not available up to 96 hours post-dose, the area under the missing terminal part of the curve will be determined by interpolation or extrapolation using a similar principle as for AUC(0-inf), where the terminal elimination rate constant, <math>\lambda_Z</math>, is used given that there are sufficient measurements for the determination of the terminal elimination rate constant.

Accumulation ratio	0–96 h post-injection at visit 7		
Accumulation ratio is calculated as AUC(0-96h) at steady state/AUC(0-96h) at single dose.

Terminal half-life (t 1/2 )	0–96 h post-injection at visit 2a and visit 7	h	
<math>t_{1/2} = \ln(2) / \lambda_Z</math>, where <math>\lambda_Z</math> is the terminal elimination rate. The terminal elimination rate will be estimated using linear regression on the terminal part of the log(activity) versus time profile.

Clearance (CL)	0–96 h post-injection at visit 2a and visit 7	mL/h/kg	
CL= Dose / AUC.    Using AUC(0-inf) for single dose and AUC(0-96h) for steady state.

Vz	0–96 h post-injection at visit 2a and visit 7	mL/kg	
Apparent volume of distribution based on the terminal phase.  <math>Vz = CL / \lambda_Z</math>

Vss	0–96 h post-injection at visit 7	mL/kg	
Apparent volume of distribution at steady-state.  <math>Vss = CL * MRT</math>

%extrap	0–96 h post-injection at visit 2a and visit 7	%	
Percentage of AUC(0-inf) determined by extrapolation.  <math>AUC_{(t-inf)} / (AUC_{(0-inf)})</math>

Statistical Analysis Plan  
 Trial ID: NN7088-4595  

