 UTN: U1111-1235-5905  
 EudraCT No: 2020-003001-58

CONFIDENTIAL

Date:  
 Version:  
 Status:  
 Page:

29 January 2021  
 2.0  
 Final  
 14 of 18

Novo Nordisk

Title	Time frame	Unit	Details
MRT	0–96 h post-injection at visit 2a and visit 7	h	Mean Residence Time. $MRT = AUMC/AUC_{(0-\infty)}$ , where AUMC is the area under the first moment curve, i.e. the area under the curve $t \cdot C_{(t)}$ , calculated with the same method as $AUC_{(0-\infty)}$ (linear trapezoidal method + extrapolated area)
$\lambda_z$	0–96 h post-injection at visit 2a and visit 7	1/h	Terminal elimination rate constant. The terminal elimination rate constant will be estimated using linear regression on the terminal part of the $\log(\text{activity})$ versus time profile

Single dose PK will be based on the PK session at visit 2a, and steady state PK will be based on the PK session at visit 7.

The PK parameters will be calculated using plasma FVIII activity obtained from the FVIII chromogenic assay. The PK parameters will be derived according to a non-compartmental method, as described in [Table 2](#). The actual time points will be used in the calculations.

If any profiles and/or individual plasma FVIII activities are excluded from the primary pharmacokinetic analysis, a sensitivity pharmacokinetic analysis will also be performed and reported based on all observed data. The primary pharmacokinetic analysis is based on the full analysis set excluding outliers.

Specifically which data points and profiles that will be excluded will be defined prior to database lock. It should exclude profiles with pre-dosing activity > 5% (possibly indicating inadequate wash out) at visit 2a and profiles that are not indicative of a normal intravenously injection (i.e. clearly increasing plasma FVIII activities initially). If a patient is treated with an additional dose during the PK session, the plasma FVIII activities after the occurrence will then be excluded. Furthermore, if the profile shows indications of an additional dose (e.g. clearly increased plasma FVIII activity), the plasma FVIII activities after the occurrence will then also be excluded.

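### The SAP's half-LLOQ substitution is not kept out of the terminal slope, so half-life and Vz can be distorted in either direction in faster-clearing patients

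*SAP*

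**What the plan says.** - SAP 5.1 gives a general rule: "FVIII activities below lower limit of quantification (LLOQ) will be set to half the value of the LLOQ". It is limited to no endpoint. Protocol section 9 does not contain it, and neither document gives the LLOQ.
- SAP 5.4.3, Table 2, on half-life: "The terminal elimination rate will be estimated using linear regression on the terminal part of the log(activity) versus time profile". The row for the rate constant repeats this. Neither row says how many points are used, how they are chosen, or what happens to values below LLOQ.
- AUC(0-t) in Table 2 does have an end limit; it runs "from time 0 to the time for the last measurable activity". Whether a half-LLOQ value counts as measurable is not said.
- Single-dose clearance is dose over AUC(0-inf), and steady-state clearance is dose over AUC(0-96h). Vz is clearance divided by the terminal rate constant.
- SAP section 4 says that the rules for excluding PK data are in the SAP. Those in 5.4.3 cover inadequate wash-out ("It should exclude profiles with pre-dosing activity > 5% (possibly indicating inadequate wash out) at visit 2a"), profiles that do not look like an intravenous injection, and additional doses. Values below LLOQ are not among them.

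**The concern.** On a log scale a substituted constant is not neutral. The 96 h sample is the last point of the regression and has high leverage, so its imputed value can largely set the slope. Only patients with low late activity are affected, and these are the patients whose half-life is of most interest. A fast-clearing patient can be given an ordinary-looking half-life, or a moderately fast one can look faster than he is.

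Half-life is a secondary PK endpoint, about 12 to 15 patients contribute, and individual values are listed. The planned PK sensitivity analysis would not show the problem: it is run only if data were excluded, and it puts data back. If the analyst instead drops such points at the pre-lock review, that is a choice made after seeing the data and outside the written rules.

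**Working it through.** The plan states no figure on this point, so there is none to reproduce.

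**Inputs.** Dose 50 IU/kg (Protocol 8.5). About 2% rise per unit (Protocol 4.1.4), so activity at time 0 is about 50 x 0.02 = 1.0 IU/mL. Post-dose samples at 0.5, 1, 4, 12, 24, 48, 72 and 96 h (Protocol Table 1-1). Assumed, because not given: LLOQ L of 0.005 to 0.05 IU/mL; mono-exponential, noise-free single-dose decline; terminal fit on the last three or last four samples.

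**When a sample falls below LLOQ.** C(96) = 2^(-96/h), with h the half-life in hours. This is below L when h < 96 ln2 / ln(1/L). The limits are 12.6 h (L = 0.005), 14.4 h (0.01), 17.0 h (0.02), 19.0 h (0.03) and 22.2 h (0.05).

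**Effect on the slope.** Let k = ln2/h.

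- Three points (48, 72, 96 h): the slope depends only on the first and last points, so k* = k + ln[C(96)/(L/2)]/48.
- Four points (24 to 96 h, centred times -36, -12, 12, 36, sum of squares 2880): substituting the 96 h value adds 36 ln[C(96)/(L/2)]/2880 = ln[C(96)/(L/2)]/80. If the 72 h value is also substituted, add ln[C(72)/(L/2)]/240.

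If only the 96 h value is substituted, half-life comes out too short when true C(96) lies between L/2 and L, and too long when it lies below L/2.

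**Worked case.** L = 0.02, h = 16 h: k = 0.04332, C(96) = 0.015625, ln(0.015625/0.01) = 0.4463.

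- Three points: k* = 0.04332 + 0.4463/48 = 0.05262, so half-life = 0.6931/0.05262 = 13.2 h.
- Four points: k* = 0.04332 + 0.4463/80 = 0.04890, so half-life = 14.2 h.

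**Further cases.** Vz and single-dose CL follow Table 2 with AUC(0-t) ending at the last measurable value. They are compared with the same calculation when values below LLOQ are left out of the slope. Paired figures are three-point / four-point.

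| LLOQ | True half-life | True C(96) | Three-point | Four-point | Vz | CL |
|---|---|---|---|---|---|---|
| 0.02 | 16 h | 0.0156 | 13.2 h (-18%) | 14.2 h (-11%) | -17% / -11% | +0.8% / +0.5% |
| 0.03 | 18 h | 0.0248 | 14.1 h (-21%) | 15.5 h (-14%) | -20% / -13% | +1.3% / +0.9% |
| 0.03 | 14.45 h | 0.0100 | 17.5 h (+21%) | 16.2 h (+12%) | +21% / +11% | -0.6% / -0.4% |
| 0.01 | 10 h | 0.0013 | 16.9 h (+69%) | 12.9 h (+29%) | +65% / +28% | -2.3% / -1.0% |

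Leaving values below LLOQ out of the slope returns the true half-life in every row.

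**Edges of the range.**

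- Just under the limit, C(96) is close to L and the three-point slope gains ln2/48. The error is then about -26% at L = 0.02 and -28% at L = 0.03 (-17% and -19% with four points).
- For L up to 0.03, overestimates above about 21% need a 96 h level below 1%, as in the last row.
- At L = 0.05 that no longer holds: a true 16 h (96 h level 1.6%) reads 20.7 h (+29%) or 17.4 h (+9%).
- At L = 0.01 or lower, no patient with a 96 h level of at least 1% is affected.

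**Clearance.** For L of 0.005 to 0.02 and half-life of 10 h or more, single-dose CL moves between about -5% and +1.5%, and steady-state CL by at most 1.9%.

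**The case against.** The best counter-argument is that entry into the slope is inferred from silence. Table 2 speaks of measurable activity for AUC(0-t) and AUC(0-inf), and of having enough measurements to determine the rate constant when AUC(0-96h) must be completed. An imputed value is not a measurement, so the table can be read as fitting measured values only. The SAP also leaves other specifications to the mock TFL, which is not available here. This stands in part: the SAP does not expressly instruct use of substituted values in the slope. But the measurability wording is attached only to the AUC rows, the rule in 5.1 is unrestricted, and the SAP says that the exclusion rules are in the SAP.

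The second objection is size, and most of it stands. LLOQ and half-life are assumptions. The protocol speaks only of the possibility of "achieving FVIII levels in the range of moderate haemophilia A with a less-burdensome every fourth day treatment regimen" and gives no numeric trough. With a low LLOQ few or no profiles may be affected. The SAP does not fix three terminal points, and four points cut the tabulated errors by roughly a third to more than a half.

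Three stronger readings are tempting but not supported:

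- That clearance is distorted too. The tail is a small share of AUC, and steady-state clearance uses AUC(0-96h).
- That one substituted point usually steepens the slope. At LLOQ 0.01 the 96 h sample alone is below LLOQ for half-lives of about 10.8 to 14.4 h, and the sign changes at 12.6 h, near the middle.
- That the trial's mean half-life would be seriously wrong. No sample of 12 to 15 patients was simulated and errors run both ways. One +69% error among 12 profiles moves the geometric mean by 1.69^(1/12) - 1, about 4.5%. No confirmatory test depends on half-life.

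**Conclusion.** The point holds for terminal half-life and Vz. An unrestricted substitution rule, together with a terminal regression that does not exclude substituted values, gives a wrong half-life when followed literally. In the tabulated cases at LLOQ 0.02 to 0.03 with a 96 h level of at least 1%, the error is 18 to 21% in either direction with three points and 11 to 14% with four. It is larger close to the LLOQ limit and in patients whose 96 h level is well below 1%. All these figures assume 1.0 IU/mL at time 0, noise-free mono-exponential decline and an LLOQ that the documents do not give. If all samples are at or above LLOQ there is no effect. The point does not extend to clearance. The change should be made because it is cheap and settles the choice before the data are seen.

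**What to change.** Add to SAP Table 2, in the rows for the terminal rate constant and AUC(0-t): 'Post-dose FVIII activities below LLOQ are not used in the regression for the terminal elimination rate constant and do not count as measurable for AUC(0-t). At least three measurable terminal points are required; otherwise the rate constant and the parameters derived from it are reported as not estimable.' Limit the rule in SAP 5.1 to summaries and the trough and recovery model, where half-LLOQ can stay, and state the assay's LLOQ.

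The cost is a few lines in the SAP and no new data. The downside is that a few profiles will use an earlier terminal window, and half-life may not be estimable in a patient with too few measurable points. Results do not change if no sample is below LLOQ.

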**Novo Nordisk**

### 5.3 Primary endpoint analysis

Endpoint title	Time frame	Unit
Number of bleeding episodes	From start of treatment until visit 7	Count

The primary endpoint will be analysed by a Poisson regression model allowing for over-dispersion (using Pearson's chi-square divided by the degrees of freedom) with the logarithm of duration of actual prophylaxis treatment with N8-GP used as offset. Estimates of the annualised bleeding rate (ABR) will be provided with 95% confidence intervals.

Only the observed bleeding episodes will be counted and the offset will be the duration of actual prophylaxis treatment with N8-GP.

A sensitivity analysis based on negative binomial regression model with the logarithm of duration of actual prophylaxis treatment with N8-GP used as offset will also be performed.

Another sensitivity analysis will be performed imputing the number of bleeding episodes for patients that discontinue treatment. For patients prematurely discontinuing treatment, the number of bleeding episodes counting in the analysis will be imputed up to what they could be expected to have had if they had completed the trial on treatment. If e.g. a patient withdraws after 2 months with 3 bleeding episodes, but the patient should have been in the study for 6 months, then this patient will in the analysis count as having had 9 bleeding episodes in 6 months. This is similar to last observation carried forward (LOCF) and will avoid positive bias occurring from patients with many bleeding episodes withdrawing early. For patients withdrawing within 1 month this method is considered to give too uncertain LOCF values, hence imputation will not be attempted for such patients. Instead only the observed bleeds and the observed duration will be used.

ABRs will be summarised in total, by cause of bleed, and by location of bleed (including ABR in baseline target joints).

Bleeding episodes in relation to surgery will not be included in the analysis.

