**Novo Nordisk**

#### 5.4.2.1 Incidence Rate of Confirmed FVIII-inhibitors $\geq 0.6$ BU

A patient is said to have FVIII-inhibitors if two consecutive tests, preferably within 2 weeks, are positive ( $\geq 0.6$  BU). The rate of inhibitors will be reported and a 1-sided 97.5% upper confidence limit will be provided based on an exact calculation for a binomial distribution. For the calculation of the inhibitor rate the numerator will include all patients with neutralising antibodies while the denominator will include all patients with a minimum of 50 exposures plus any patients with less than 50 exposures but with neutralising inhibitors.

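### Sub-analyses of the bleeding rate with no bleeds get no confidence interval, although an exact upper limit needs only the prophylaxis time already recorded (minor reporting point)

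*SAP*

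**What the plan says.** SAP 5.3 (and protocol 9.4.2 in the same terms) analyses the number of bleeds with a Poisson regression that allows for over-dispersion. It promises an interval without exception: "Estimates of the annualised bleeding rate (ABR) will be provided with 95% confidence intervals". Exposure is actual time on treatment: "Only the observed bleeding episodes will be counted and the offset will be the duration of actual prophylaxis treatment with N8-GP". ABRs are also to be summarised by cause and by location of bleed, including baseline target joints. SAP 5.1 adds that summaries and analyses are in general repeated by age group (12-17 and 18-70 years).

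SAP 5.1 then sets two limits on the ABR sub-analyses. The first concerns small groups: "In the sub analyses of annualised bleeding rate where there are less than 5 patients in a sub-group, model based estimation will not be done". The second concerns groups without events: "If no bleedings occur in a sub-group, then the confidence interval will not be calculated". No reason and no substitute are given for the second.

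For the inhibitor rate, SAP 5.4.2.1 takes another course: "a 1-sided 97.5% upper confidence limit will be provided based on an exact calculation for a binomial distribution". It makes no exception for zero cases.

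**The concern.** The rule removes the interval for one outcome only, and it is the best one. A subgroup of at least five patients with a single bleed gets an estimate with an interval; a subgroup with none gets no interval. The cause is a limit of the fitted model. It is not a lack of information, because patients and person-time are known whether or not anyone bled.

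No hypothesis is tested and no sample size was calculated, so estimates with their precision are the trial's main quantitative output. A zero in a small cell without an upper limit invites more confidence than a few patients over 28 weeks can support. The SAP already accepts, for inhibitors, that zero events still call for an upper limit.

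**Working it through.** The plan gives no figure for this point, so there is none to reproduce.

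**Inputs from the documents**
- Treatment of at least 28 weeks and 36 patients planned (SAP 1.2).
- 95% intervals for the ABR, with actual prophylaxis time as offset (SAP 5.3). Sidedness is not stated; I take the interval as two-sided, which leaves 0.025 in the upper tail.
- In the global programme, 40% of adults and adolescents were bleed-free on prophylaxis and the median spontaneous rate was 0.00 (protocol 2.2).

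**Assumptions**
- Subgroup sizes are not in the documents, so a range is shown.
- Every patient contributes exactly 28 weeks: 196/365.25 = 0.5366 years.
- Cause and location cells count as subgroups under SAP 5.1, which does not define the term.

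**Step 1. Why the model gives nothing.** With a log link the fitted rate is exp(b). With no bleeds the best fit drives b to minus infinity, so no Wald interval exists. The Pearson dispersion is undefined as well. A test fit with eight patients and no bleeds stopped with an error.

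**Step 2. The exact Poisson limit.** For rate r and total time T, the chance of no bleeds is exp(-rT). Setting this to 0.025 gives r = -ln(0.025)/T = 3.689/T. The lower limit is 0.

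**Step 3. Over-dispersion.** Take a negative binomial with mean m per patient over 28 weeks and variance m + k·m². The chance of no bleeds in n patients is (1 + k·m)^(-n/k). Setting this to 0.025 gives m = (0.025^(-k/n) - 1)/k, and division by 0.5366 makes it annual. The documents give no k; 1 and 2 are assumed.

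| Patients | T (years) | Poisson limit | k = 1 | k = 2 |
|---|---|---|---|---|
| 3 | 1.61 | 2.29 | 4.51 | 9.97 |
| 5 | 2.68 | 1.37 | 2.03 | 3.14 |
| 10 | 5.37 | 0.69 | 0.83 | 1.02 |
| 20 | 10.73 | 0.34 | 0.38 | 0.42 |
| 36 | 19.32 | 0.19 | 0.20 | 0.21 |

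For example, at n = 5: 3.689/(5 × 0.5366) = 1.37 bleeds/year. At n = 36: 3.689/(36 × 0.5366) = 0.19.

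**Step 4. Where zeros would occur.** If 40% of patients are bleed-free, independently of each other, a whole age group of 5 has no bleeds with probability 0.4^5 = 0.010, and a group of 10 with 0.4^10 = 0.0001. Zeros are more plausible in cells that count only one type or site of bleed. A cause or location split does not reduce the number of patients, however. Unless the cell is limited to a subset, T is that of the whole trial and the limit is near 0.19. Zeros and wide limits coincide mainly when such a cell is crossed with a small age group, or is confined to few patients with a baseline target joint.

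**Step 5. The SAP's own practice.** Under SAP 5.4.2.1, zero inhibitors in 30 patients would be reported with an upper limit of 1 - 0.025^(1/30) = 11.6%, and zero in 36 with 9.7%.

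**The case against.** The rule is openly pre-specified and confined to sub-analyses. If patient-years are tabulated, any reader can work out 3.689/T. The inhibitor precedent is imperfect: that outcome is one yes or no per patient, which suits a binomial, whereas bleeds recur and the SAP explicitly allows for over-dispersion. A pure Poisson limit drops that allowance. At n = 5 it gives 1.37 where an assumed k of 1 to 2 gives 2.0 to 3.1.

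All of this stands, and it limits the weight of the point. It does not justify the rule: an upper limit labelled as probably too low says more than no limit.

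Three stronger readings are tempting, and the documents do not support them.
- A reader might infer that cells with wide limits will often be empty. Step 4 shows otherwise: whole age groups are rarely empty, and full-cohort cause or location cells, where zeros are more plausible, have narrow limits.
- A reader might note that 1.37 exceeds the median ABR of 1.18 in protocol 2.2. That figure is a median of patients' individual rates, while the limit bounds a mean rate, so it is not a fair yardstick.
- A reader might infer that tables will show a bare ABR of 0. SAP 5.1 says only that the interval is not calculated. Layout is left to the mock tables, which are not among the documents, and summaries of continuous endpoints are to include N.

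**Conclusion.** The point holds as a minor reporting improvement. SAP 5.1 leaves the most favourable ABR sub-analyses without a statement of precision, although the exact limit needs only data the analysis already uses. The loss ranges from small (limit 0.19 bleeds/year with all 36 patients) to material (1.37 with 5, more under over-dispersion).

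These figures rest on assumed subgroup sizes, exactly 28 weeks per patient and, for the wider limits, an assumed k. The 1% figure for an age group of 5 also assumes independence and carries the 40% bleed-free share over from earlier trial parts whose duration protocol 2.2 does not give. The overall primary ABR and its interval are not affected.

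**What to change.** Replace the zero-bleed sentence in SAP 5.1 with:

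*If no bleeds occur in a subgroup, the number of patients, total prophylaxis time and a 1-sided 97.5% exact Poisson upper limit (3.689 divided by total prophylaxis time in years) are reported; this applies also to subgroups with fewer than 5 patients, because no model is fitted.*

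Add a table footnote that the limit does not allow for over-dispersion and is therefore probably too low. Naming one method now avoids a choice after the data are seen, and the last clause settles how the sentence fits with the adjoining five-patient rule.

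The cost is one SAP sentence, a footnote and a few lines of code. It needs no new data and no change to trial conduct. The downside is that the Poisson limit is too narrow under over-dispersion, most of all in the smallest groups: at n = 3 it is 2.29, against 4.51 with k = 1.
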